| Intervention | For every adult (a "case") tested positive by RTqPCR, up to 45 mL of blood will be taken, a nasal swab and an oropharyngeal swab will be performed, an induced sputum (or saliva), hair sample and a stool samples will be recovered at the inclusion. As follow-up, 6 months, 15 months and 24 months after inclusion, the same sampling will be performed. Two additional sampling visits will be proposed to adult participants with a reinfection or a post-vaccination infection at 3 weeks and at 2 months. For every child tested positive by RTqPCR, up to 50 mL of blood will be taken, a nasal swab, oro- and naso-pharyngeal swabs, induced sputum or saliva, hair sample, as well as a stool sample will be obtained at inclusion. The follow up visits at 6, 15 and 24 months after inclusion, will include the same samples. For patients at home, an experienced nurse from CIEC will perform the sampling, using all the required precautions and protections in the actual context. For hospitalised patients, a simplified sampling strategy will be put in place and adapted to the patient state, the workload of staff and adapted constantly depending on the evolution of the epidemy. Below is described the maximal sampling strategy. |
| Study timelines | 
 ● Recruitment period: up to 29 months (March 2020-August 2022) - to be adapted to the evolution of the epidemiological situation) First patient in: March 2020 ● Follow-up period : max 24 months ● Analysis of results and study report: 3 months ● Global duration: 54 months (to be adapted on the duration of the epidemiological situation) |
| Population | Predi-COVID Inclusion criteria: |

| | |
|--|---|
| | 
 • Signed informed consent form • Adult (≥ 18 years old), child and adolescent (0-17 years old) patients with confirmed SARS-CoV-2 infection as determined by PCR, performed by one of the certified laboratories in Luxembourg • Hospitalized or at home 
Exclusions criteria :
 
 • Patients not understanding French or German • |
| Patient withdrawal criteria | Transfer outside Luxembourg if no information can be collected in the receiving country. |

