3.2 Secondary objectives

Secondary objectives include

- to study the long term (up to 2 Year) health consequences of COVID-19.
- to characterise clinical symptoms and biological markers for individuals with re-infection/infection post-vaccination and Long COVID
- to describe the trajectories of symptoms after being positively diagnosed to COVID-19
- to identify vocal biomarkers associated with respiratory syndromes, fatigue, anxiety or emotions related to COVID-19 which could then further be used for easy remote monitoring of COVID-19 patients.
- to identify the virological factors and the individual characteristics involved in viral escape to COVID-19 vaccines and in reinfections
- to characterize the cellular and antibody responses (type and durability) elicited by vaccines and in uninfected and recovered COVID-19 patients (either vaccinated or not) with an emphasis on the variability of immune responses

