| Si oui: Quel type de test a été fait? (PCR, Rapid LAMP test, test antigénique rapide/test sérologique / ne sait pas) |
| Si oui: Au moment des tests aviez-vous des symptômes? |
| Si oui: Avez-vous été hospitalisé pour Covid-19? |
| Si oui: Un membre de votre foyer a-t-il été testé positif pendant cette même période? |
| Si oui: Quel est l'âge des membres du foyer testés positifs (vous inclus) |
| Participez-vous ou avez-vous participé à une autre étude en lien avec Covid-19? (SéroCov2, Convince, Prédicovid, Orchestra, Cov-Escape, autre?) |

Vaccination

| | |
|-------------------------------------|---------|
| Etes-vous vaccinés contre COVID-19? | oui/non |
|-------------------------------------|---------|

| | |
|---|--|
| Si oui: quand?(dates doses) | |
| Si oui zone de vaccination | |
| Si oui : Connaissez-vous la marque de vaccin? | |
| Si 2nd dose pas faite, raison? | |
| Si oui: Avez-vous eu des effets secondaires après la vaccination? | |
| Si oui: Spécifier le type d'effets secondaires : | |
| Réactions au niveau du site d'injection : | Oui/Non |
| rougeur | Oui/Non |
| chaleur | Oui/Non |
| douleur | Oui/Non |
| démangeaisons | Oui/Non |
| hématome | Oui/Non |
| gonflement | Oui/Non |
| induration | Oui/Non |
| ecchymose | Oui/Non |
| sensibilité | Oui/Non |
| Effets secondaires systémiques : | |
| Avez-vous eu un gonflement important des membres? | oui/non |
| Fièvre | oui/non |
| Frissons | oui/non |
| Maux de têtes | oui/non |
| Nausée/vertige | oui/non |
| Augmentation soudaine de fatigue / Malaise | oui/non |
| Douleurs musculaires | oui/non |
| Douleurs articulaires | oui/non |
| Réaction cutanée (éruption, peau qui brûle..) | oui/non |
| Arythmies | oui/non |
| Myocardites | oui/non |
| Péricardites | Oui/non |
| Autre effet indésirable? spécifier | oui/non |
| Si oui après dose 2, combien de temps a duré cet effet indésirable? | Less than 1 day / 1 day / 2 days / 3 days / 4 days / 5 days / 6 days / 1 week / 2 weeks / 1 month / Still unresolved |

| | |
|---|--|
| Si oui après dose 1, combien de temps a duré cet effet indésirable? | Less than 1 day / 1 day / 2 days / 3 days / 4 days / 5 days / 6 days / 1 week / 2 weeks / 1 month / Still unresolved |
| Date des premiers effets indésirables après dose 1 | |
| Date des premiers effets indésirables après dose 2 | |
| Avez-vous été vacciné contre la grippe saisonnière? | oui / non / ne sais pas |
| Si oui date de vaccination | |

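### The Annex 3 vaccination module asks the vaccine brand once and has dose-specific items for doses 1 and 2 only, so brand cannot be reliably linked to individual doses

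*Protocol*

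**What the plan says.** All of the following is in the protocol.

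- **Annex 3, complementary modules, Vaccination.** After asking whether the participant is vaccinated, the form asks when: "Si oui: quand?(dates doses", plural, with an empty answer cell. Brand is one singular item, "Connaissez-vous la marque de vaccin", also with an empty cell. The next row asks why a second dose was not given: "Si 2nd dose pas faite, raison".
- **Same module, side effects.** A single checklist covers the whole course. Duration and onset are then asked by dose, the onset rows being "Date des premiers effets indésirables après dose 1" and "Date des premiers effets indésirables après dose 2". No row names a later dose.
- **Section 3.2.** One secondary objective is "to characterize the cellular and antibody responses (type and durability) elicited by vaccines", in uninfected and recovered people, with an emphasis on variability of response. Another is "to identify the virological factors and the individual characteristics involved in viral escape to COVID-19 vaccines and in reinfections".
- **Synopsis, Study timelines.** "Recruitment period: up to 29 months (March 2020-August 2022".
- **Section 6.** Adults with a reinfection or a post-vaccination infection are offered two extra sampling visits, at 3 weeks and 2 months.
- **Section 10 and the introduction to Annex 3.** A trained nurse or CRA completes the adapted CRF, and the complementary modules are filled in with the patient.
- **Section 11.4.** No analysis by vaccine brand is described, and no rule assigns a response to a particular vaccine.

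**The concern.** To interpret an antibody or cellular response, or an infection after vaccination, the analyst needs to know which product was given, at which dose, and when. The form can collect several dates but asks for brand as a property of the whole course. If a participant had doses of different brands, nothing on the form says which brand goes with which date. If there was a further dose after the second, no item asks for it.

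What is at stake is the quality of one exposure variable for two secondary objectives. An ambiguous or wrongly coded vaccine history blurs the description of responses. Because Section 3.2 emphasises variability between people, some variation that comes from the vaccine schedule could be read as individual variation. A statistical analysis plan can set rules for handling ambiguous records, but it cannot supply a link between brand and dose that nobody recorded.

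**Working it through.** The protocol states no figure on this point, so there is nothing to reproduce. The check is a reading of the form, item by item, against the use planned for it.

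**1. Count of items in the COVID-19 vaccination block (Annex 3).**

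| Item | Number |
|---|---|
| Dose dates, open line, no stated maximum | 1 |
| Brand, whole course | 1 |
| Reason for no second dose | 1 |
| Duration of side effects (dose 1, dose 2) | 2 |
| Onset date of side effects (dose 1, dose 2) | 2 |
| Brand for a given dose | 0 |
| Any item naming dose 3 or later | 0 |

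**2. What can be recovered from a completed form.** Take three hypothetical participants.

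- *Two doses, one brand.* Two dates and one name. The history is readable, provided one assumes that the name applies to both doses.
- *Two doses, two brands.* If only one name is entered, the record looks the same as the first case. If both names are written in, there are 2 possible orders and the form does not say which is right.
- *Three doses, two brands.* If three dates and two names are written in, each dose could be either brand. That gives 2 × 2 × 2 = 8 combinations, less the 2 that use only one brand, so 6 histories fit the same entry. If the third date is not written in, no other item on the form shows that it is missing.

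These cases show where the record becomes ambiguous. They say nothing about how often it happens.

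**3. Whether another form shown fills the gap.** Under the schedule in Section 7.1, CRF data for patients at home are collected once, at baseline. The follow-up questionnaires printed in Annex 2 contain no vaccination item. The detailed long-COVID questionnaires are not reproduced, so nothing can be said about them. The linkage to social-security data in Section 2.6 is described for care pathways, costs and work, and vaccination records are not mentioned.

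**4. Comparison within the same annex.** The Covid-19 status part asks for a date for every positive test when there were several. Repeated recording by event was therefore used for prior infection. The vaccination part does the same for dates but not for brand.

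**5. Set against the objectives.** Vaccinated or not, and dose dates, are collected. Those are the items most directly needed for the grouping that Section 3.2 names and for durability. Product by dose, and a prompted record of doses beyond the second, are not collected in structured form.

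**The case against.** **The open cells may be enough.** The date line is plural and sets no limit, so a third date can be entered. The brand cell shows no list and no one-answer limit, so two names can be entered. The annex is a text rendering of an electronic form whose field types are not shown, and a trained nurse or CRA fills in the module with the patient and can clarify. This stands. A reader might infer that mixed-brand and booster schedules cannot be identified at all, and the documents do not support that. The narrower point remains: nothing in the printed form asks for the link between brand and dose, so capturing it depends on the initiative of whoever completes the form.

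**No brand analysis is planned.** Section 3.2 speaks of characterising responses and identifying factors; it does not mention brand. Section 11.4 has no analysis by brand. This also stands. A reader might infer that immune responses will be credited to the wrong vaccine, but no assignment rule exists from which that would follow. The likelier result is missing or ambiguous brand-by-dose data, with misclassification possible.

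**The harm can be repaired.** A reader might conclude that the information is lost for good once the form is completed. It is not: participants can be asked again, and Section 7.1 has visits at 6, 15 and 24 months. That limits the damage, provided that someone does ask.

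**The side-effect rows are peripheral.** One checklist for the whole course sits awkwardly beside duration and onset by dose, so an effect cannot be matched to its dose. But no stated objective or evaluation criterion uses vaccine side effects, so this has no consequence for the planned results.

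**Conclusion.** The point holds in limited form. As printed, the module does not reliably link brand to dose, and it records doses after the second only if they are written into the open date line. Vaccine exposure may therefore be ambiguous or misclassified for the two secondary objectives on vaccine-elicited responses and viral escape. The primary objective, the main evaluation criteria and the sample-size statements are untouched.

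The size cannot be calculated from the documents. A reader might try by assuming that a share m of participants labelled with one brand had a mixed course and a response midway between brands. A difference between brands would then shrink to (1 − m) of its true value, and the number needed would rise by 1/(1 − m)². For m from 0.1 to 0.4 that gives 1/0.81 = 1.23 to 1/0.36 = 2.78. The arithmetic is right, but it should not be quoted as an effect on this study. The share and the midpoint response are both assumed, it takes for granted that every mixed course is labelled with one brand, and the protocol neither plans nor powers a contrast between brands.

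The conclusion rests on the form as printed. If the electronic version already repeats date and brand for each dose, the point falls away and only the annex needs updating. Otherwise it is a cheap improvement worth making.

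**What to change.** Replace the single date line and the single brand line with a block repeated for each dose received before the inclusion PCR, with no upper limit on the number of doses. Each block records dose number, date, and brand from a list that includes unknown. Take the entries from the vaccination certificate where it is available and from the interview otherwise. For participants already enrolled, complete the block at their next contact, for example a scheduled sampling visit.

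Moving the side-effect checklist, onset and duration inside the block would let each effect be matched to its dose. This is optional, since no stated objective uses these items.

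The cost is a small change to the eCRF and its codebook, one or two more minutes of interview (an estimate, not a figure from the protocol), and the effort of asking enrolled participants again.

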ANNEX 4 :

COLLECTE DE DONNEES PREDI-COVID

Utilisation de l'application smartphone

CoLive LIH (optionnel)

Français

V1.0

Suivi à distance depuis un smartphone ou tablette :

- 1 enregistrement vocal tous les jours de J0-J14 puis une fois par semaine dans les semaines 3 et 4, puis une fois par mois de M2 à M12

Table des matières

[figure not shown]
[Enregistrement de la voix sur smartphone](#)

Enregistrement de la voix sur smartphone

Pour l'identification de biomarqueurs vocaux associés à un syndrome respiratoire, la fatigue, à l'anxiété ou aux émotions en lien avec Covid19

Composé de 2 enregistrements

1. Enregistrement standardisé d'un texte pendant 30 secondes
2. Enregistrement d'un son "AAAAA" le plus longtemps possible par l'individu sans reprendre sa respiration.

Only for up to 300 household members of Predi-Covid participants

ANNEX 5 :

QUESTIONNAIRE PREDI-COVID-H

Utilisation du module e-PRO de Ennov Clinical

Questionnaires français

V1.0

Suivi à distance depuis un smartphone, tablette ou ordinateur :

- 1 questionnaire court par jour tant qu'il n'y a pas eu de confirmation de Covid19 par test positif et pendant 14 jours

Table des matières

[Système d'alerte](#)

[Questionnaire quotidien](#)

[Questionnaire permanent](#)

[Profil](#)

Questionnaire quotidien

Mon état de santé général

Vous êtes un membre du foyer d'une personne diagnostiqué positif à Covid19. Veuillez remplir ce questionnaire de suivi quotidien.

1) Date du questionnaire :

2) Avez-vous été testé et diagnostiqué positif à Covid19 ? Oui/Non

3) Vous êtes: A la maison / A l'hôpital / Autre

Si A l'hôpital : Lequel : menu déroulant

Centre Hospitalier de Luxembourg / Fondation Hôpitaux Robert Schuman / Centre Hospitalier Emile Mayrisch / Centre Hospitalier du Nord / Autre

4) Comment vous sentez-vous aujourd'hui ? Je me sens bien / Je me sens fatigué(e) / Je me sens mal

5) Avez-vous bien dormi ? Oui/Non

Si non, pourquoi ? [Champ libre]

6) Avez-vous une toux sèche ? Oui/Non

7) Avez-vous une augmentation de votre toux habituelle ces derniers jours ? Oui/Non

8) Avez-vous un mal de gorge apparu ces derniers jours ? Oui/Non

9) Avez-vous noté une forte diminution ou perte de votre goût ou de votre odorat ? Oui/Non

10) Avez-vous de la diarrhée ? Avec au moins 3 selles liquides/molles par jour. Oui/Non

11) Avez-vous des douleurs musculaires ou des courbatures inhabituelles ces derniers jours ? Oui/Non

12) Avez-vous des douleurs thoraciques ces derniers jours ? Oui/Non

13) Quel est votre niveau de douleur actuel ? (Notez de 1 à 10)

14) Avez-vous de la fièvre ? Oui/Non

Avez-vous un thermomètre ? Oui/ Non

Si oui, Veuillez prendre votre température :

15) Avez-vous des difficultés respiratoires ? Oui/Non

16) Avez-vous vu apparaître une gêne respiratoire ou une augmentation de votre gêne respiratoire habituelle ? Oui/Non

17) Quel est votre poids ? (se peser sans chaussure) __ kg ou Je ne sais pas

18) Avez-vous des difficultés importantes pour vous alimenter ou boire ? Oui/Non

19) Avez-vous d'autres symptômes ? Oui/Non

Si oui, veuillez préciser lesquels : [champ libre]

Questionnaire permanent

A ne remplir qu'une fois

Profil

-
- Sexe
- Date de naissance
- Poids (kg)
- Avant le diagnostic de Covid19, avez-vous perdu, sans le vouloir, 3 kg ou plus dans les 6 derniers mois ? (Oui/non)
- Taille (cm)
- Groupe Sanguin/Rhésus
- Avez-vous
 - De l'hypertension ? Oui/Non
 - Du diabète (type 1 ou type 2) ? Oui/Non
 - Eu un cancer ? Oui/Non
 - Une maladie respiratoire ou êtes-vous suivi par un pneumologue ? Oui/Non
 - Une insuffisance rénale chronique dialysée ? Oui/Non
 - Une maladie chronique du foie ? Oui/Non
 - Une maladie connue pour diminuer vos défenses immunitaires ? Oui/Non
- Etes-vous enceinte ? Oui/Non/Non applicable
- Prenez-vous un traitement immunosuppresseur ? C'est un traitement qui diminue vos défenses contre les infections. Voici quelques exemples : corticoïdes, méthotrexate, ciclosporine, tacrolimus, azathioprine, cyclophosphamide (liste non exhaustive). Oui/Non
